Our central hypothesis is that the attending nurse will enhance critical patient-centered elements of care that will in turn improve patient education and shared decision-making, medication adherence, stroke-related health literacy, and reduce early readmissions to ultimately yield improved patient quality of life. Our primary objective is to determine whether the attending nurse model of care improves stroke patients' health at 7 days, 30 days, and 90 days after hospital discharge as assessed through questionnaires.

**Number of
Patients**

372 patients

Main Inclusion and Exclusion Criteria	
We will include all adult patients admitted to the Vascular Neurology Service with a clinical diagnosis of stroke, brain hemorrhage, or transient ischemic attack.
 
We will exclude patients whose level of care is limited to comfort care or hospice, those with severe dementia prior to admission, and those who are both non-communicative and have no family or other social support.

Investigational Product	
None
 
This is a comparative effectiveness study comparing two models of nursing care delivery to stroke patients (attending nurse model vs. conventional inpatient nursing care)

Duration of administration (if applicable)	
The duration of the intervention phase will depend on the duration of a patient's hospital admission.

Reference therapy	
The reference therapy is standard inpatient nursing care.

Statistical Methodology	
Our primary outcome will be scores on scales of medication adherence and stroke education retention. The scores on these tests will be compared between patients who were assigned to the attending nurse model of care versus standard nursing care.
 
Secondary outcomes will include comparisons between groups of the thirty day readmission rate, scores on a patient-centered stroke impact scale, 2 modified quality of life scales, results of a newly designed series of 13 Likert style questions, and a global statistic that includes the results of all scales.

Safety Evaluations	
All enrolled patients will be evaluated via telephone interview at 7, 30, and 90 days following hospital discharge and screened for major cardiovascular and cerebrovascular events. While in the hospital, subject safety will be assured via already existent quality assurance mechanisms.

Data and Safety Monitoring Plan	
The PIs will be responsible for monitoring the data quality and the ongoing safety of patients.

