2.1 Primary Objective

- To determine whether patients report better understanding of stroke facts and medication adherence when cared for by an attending nurse compared to routine nursing care.

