3.2 Study Endpoints

3.2.1 Primary Study Endpoints

- Primary endpoints will be stroke education retention as measured by the SPER and medication adherence as measured by MMAS-4 as these are the areas where we anticipate the largest potential effect of the nurse attending. The mean scores on these two tests will be compared between groups at each time interval that they are administered.

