6.3 Follow Up Phase of the Study

Follow-up visits will be conducted by telephone only. Informed consent for phone interviews will be obtained prior to the interview. Consent will also be obtained for data collection from the patients Hospital of the University of Pennsylvania electronic medical record. Whether the patient, a family member, or other person is answering the pertinent survey questions will be recorded. Patients may become fatigued when answering the survey questions in which case they can simply ask to stop and the phone conversation will end.

6.3.1 7 days following discharge

At 7 days after hospital discharge, the MMAS-4, SPER, the exploratory 13 Likert-style questions and two modified overall health questions will be administered. There are no well validated surveys regarding the inpatient experience that are patient centered and stroke specific so we designed 13 questions which focus on subject's perception of their inpatient stay as well questions designed to assess quality of life following stroke. The newly devised Likert-style questions as well as the 2 modified overall quality of health questions have been reviewed by a stroke-survivor in her role as patient advocate who was cared for at our institution. The single health literacy question will also be repeated at the 7 day follow up visit and interviewees will be asked about readmission. Though ideally patients will answer all survey questions themselves, responses to survey questions will be accepted from a legal representative provided they can answer accurately. Each interviewee will be identified based on their relationship to the patient on survey collection forms.

6.3.2 30 days following discharge

At 30 days following hospital discharge, the SIS and the MMAS-4 will be administered. Inquiry as to whether or not the patient has been readmitted will occur.

6.3.3 90 days following discharge

At 90 days following hospital discharge, the MMAS-4, SPER, the exploratory 13 Likert-style questions and the 2 modified global quality of health questions will be administered again. Patients will also be asked about any readmissions.

6.4 *Unscheduled Visits*

Clinic visits and other unscheduled visits will not replace phone interviews and will be entirely separate from this study.

6.5 *Subject Withdrawal*

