7.1 Primary Endpoint

The primary endpoint for this study will be a comparison of the mean scores on the SPER and the rate of adherence on the MMAS-4 (score < 2) and the SPER between groups at 7 and again at 90 days.

Scores on the MMAS-4 and SPER will be calculated per protocol. On the MMAS-4, affirmative answers will receive a point and negative answers will be assigned zero. The total score will be the sum of the answer to all four questions. The SPER, question 1 and 2 are scored as follows: 0 = no correct content in response to the question, 1 = the patient provided some but not all of the correct content in response to the question, and 2 = patient provided all key content in response to the question. Question 3-5 were scored as follows as 0 = no correct content in response to the question and 2 = the patient provided the correct response to the questions. A score of 10 indicates all correct responses to the key content.

The SIS is a patient-based, self-report scale in which each item is rated in a 5- point Likert scale in terms of the difficulty the patient has experienced in completing each item. A score of 1 = an inability to complete the item and a score of 5 = no difficulty experienced at all. Using an algorithm, summative scores are generated for each domain.

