7.3 Sample Size and Power Determination

For this pilot project, we anticipate that 65% of patients in the control arm will be adherent to medications (MMAS-4 < 2) based on literature reporting 60%¹⁶ adherence as evaluated using these scales in stroke patients and 70%²¹ adherence in patients with hypertension. To achieve success on the primary endpoint, we estimate that patients must improve to by 15% in order to make this intervention worthy of future investigation in a larger study. Assuming an alpha of 0.05 and a power of 80%, with a 1:1 assignment to each arm, we will require 186 patients in each arm for a total of 372 patients. With that number of patients

we will be able to powered to detect a very small difference of 0.3 (delta = .15 (SD=2)) in the mean scores of the SPER based on the published data.¹⁷ Each outcome will be evaluated independently so that we will not need to make any power readjustments. Readmission rates at 30 days are typically low⁴ and likely lower at our institution based on prior data so we will be underpowered for this outcome. Clinically differences on the SIS will depend on the initial stroke severity of patients within each group and therefore the study cannot be powered for this secondary endpoint.

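### Two primary scales are each tested at two times at an unadjusted 0.05 with no rule for combining the results, and Sections 3.2.1 and 7.1 define the MMAS-4 endpoint differently

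*Combined protocol and SAP*

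**What the plan says.** **Endpoints and times.** Section 7.1 takes as primary the SPER mean and "the rate of adherence on the MMAS-4 (score < 2) and the SPER between groups at 7 and again at 90 days". That is four comparisons. Section 3.2.1 also names both scales as primary but says: "The mean scores on these two tests will be compared between groups at each time interval that they are administered". Section 6.3.2 adds an MMAS-4 administration: "At 30 days following hospital discharge, the SIS and the MMAS-4 will be administered". SPER is given only at days 7 and 90, so Section 3.2.1 implies five comparisons, with MMAS-4 as a mean.

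**Form of MMAS-4.** Sections 7.1 and 7.3 use the proportion scoring below 2, and Section 7.4 tests the proportion adherent by Pearson chi-square. Only Section 3.2.1 calls for a mean. The Study Summary says "Our primary outcome will be scores on scales of medication adherence and stroke education retention" and sets the primary objective on "health at 7 days, 30 days, and 90 days after hospital discharge as assessed through questionnaires".

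**Error control.** The only alpha is 0.05, in Section 7.3, with no sidedness. The only sentence on several outcomes is "Each outcome will be evaluated independently so that we will not need to make any power readjustments". There is no hierarchy, adjustment or co-primary rule. The global statistic is a secondary outcome.

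**Success.** Section 7.3 says "To achieve success on the primary endpoint, we estimate that patients must improve to by 15" per cent. This refers to MMAS-4 adherence, names no time and does not say how SPER counts. Section 2.1 joins the scales: "better understanding of stroke facts and medication adherence when cared for by an attending nurse".

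**Day 7.** Section 3.1 calls the day-7 call the baseline assessment, while Section 7.1 makes day 7 a primary time.

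**The concern.** Testing each outcome separately at 0.05 fixes the error rate of each test. It does not fix the error rate of a conclusion that can rest on either of two times, or on either of two scales. Section 7.3 offers independent evaluation as the reason why nothing needs adjusting, but unadjusted separate testing is what raises the chance of at least one false positive.

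The plan also leaves open which results amount to success, at which time, and (through Section 3.2.1) in which form MMAS-4 is analysed. Those choices could be made after the results are known. They bear on the decision whether a larger study is worthwhile, which Section 7.3 names as the purpose, and on what is reported from a study that Section 3.1 calls phase III.

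**Working it through.** **Inputs from the protocol.** Two primary scales (3.2.1, 7.1); days 7 and 90 (7.1), plus day 30 for MMAS-4 under 3.2.1 (6.3.2); alpha 0.05, power 80%, control adherence 65%, improvement 15%, 186 per arm, SPER SD 2 and SPER difference 0.3 (all 7.3).

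**Assumptions, because the protocol gives no figure.** Two-sided tests; correlation between test statistics of 0–0.9 over time within a scale and 0–0.5 between scales, with the cross-scale, cross-time value equal to the product of the two.

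**The plan's own figure.** For 65% vs 80%, two-sided 0.05 and 80% power:
n = [1.96√(2×0.725×0.275) + 0.8416√(0.65×0.35 + 0.80×0.20)]² / 0.15² = (1.238 + 0.524)² / 0.0225 ≈ 138 per arm.
The stated 186 is not reproduced. That is a separate matter; 186 is taken as given below.

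**Separate conclusions per scale, two times.** With independent tests, either direction: 1 − 0.95² = 9.75%; favouring the nurse: 1 − 0.975² = 4.9%. Simulation of correlated normal statistics gives:

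| Correlation over time | Either direction | Favouring nurse |
|---|---|---|
| 0.3 | 9.5% | 4.8% |
| 0.5 | 9.1% | 4.5% |
| 0.7 | 8.3% | 4.2% |
| 0.9 | 7.0% | 3.5% |

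If MMAS-4 at day 30 also counts (3.2.1), the three-time rate for that scale is 14.3% if independent (1 − 0.95³) and 8.4% at correlation 0.9.

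**Any one of the four tests in 7.1.** Independent: 1 − 0.95⁴ = 18.5%; favouring the nurse: 1 − 0.975⁴ = 9.6%. With correlations (over time, between scales): (0.5, 0.3) 16.9% and 8.5%; (0.7, 0.3) 15.6% and 7.8%; (0.9, 0.5) 12.6% and 6.3%. The low end is not a bound: with every correlation at 0.8 the rates are 11.4% and 5.7%.

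**15% as an added observed threshold for MMAS-4 (absolute).** Null standard error at 65%: √(2×0.65×0.35/186) = 0.0495. Then z = 0.15/0.0495 = 3.03, a one-sided probability of 0.12% at one time and at most 0.24% over two. Adding unadjusted SPER at two times, any success favouring the nurse has probability 1 − 0.975²×0.9988² = 5.2% if independent, falling to about 3.6% at (0.9, 0.5).

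**All tests must succeed.** No inflation. Power for all four is 52–69% if the SPER difference is 0.58, adherence is 65% vs 80%, and effects are the same at both times.

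**Power at alpha 0.05 and 0.025 (186 evaluable per arm unless stated).**
- MMAS-4, absolute 15% (65% vs 80%): (0.15 − 1.96×0.0463)/0.0456 = 1.30, power 90.3%; with 2.241 in place of 1.96, 1.01, power 84.4%. With an assumed 15% loss (158 per arm): 85.1% and 77.5%.
- MMAS-4, relative 15% (65% × 1.15 = 74.75%): (0.0975 − 1.96×0.0476)/0.0473 = 0.09, power 53.6%; at 0.025, 42.3%.
- SPER difference detectable with 80% power: (1.96 + 0.8416)×2×√(2/186) = 0.58; at 0.025, (2.241 + 0.8416)×2×√(2/186) = 0.64.
- Both scales significant at 0.05 at one time, correlation 0–0.5, absolute 15%: 72–75% if the SPER difference is 0.58; 28–30% if it is 0.3.

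**The case against.** The strongest reply is that knowledge and adherence are separate questions and the plan says that it evaluates them independently, so no adjustment across scales is owed. That is a fair reading and the one that fits Section 7.3 best. It does not cover two primary times within each scale, where 7–10% remains.

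A reader might infer that the trial's false-positive rate is 13–19%, or as much as 23% with five tests (1 − 0.95⁵ = 22.6%). The protocol does not support this as a headline. No section says that one positive test out of four makes the trial a success, and the five-test count requires Section 3.2.1 to override the statistical section. These figures show what an unstated rule would cost.

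The 15% may be an observed success threshold. Section 7.3 can be read that way, and error on MMAS-4 would then be small. SPER over two times would still be uncontrolled.

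Success may require every test, since Sections 2.1 and 7.1 join the scales with *and*. There would then be no inflation, but the plan does not say so.

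The MMAS-4 mean in Section 3.2.1 may be a drafting slip: three statistical sections agree on the proportion, and the Study Summary's word for scores is compatible with a cut-off. That makes it easy to correct, but it is still a contradiction in the definition of a primary endpoint.

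Section 7.3 calls the study a pilot, which softens the consequence. The phase III label in Section 3.1 points the other way.

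**Conclusion.** Wrong as written. Two sections define the MMAS-4 primary endpoint differently, and the reason given for making no adjustment does not control error over times or over scales.

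The size depends on the success rule, which the plan leaves open. On the best-supported reading it is about 7–10% per scale in either direction, and 3.5–5% for a false finding in favour of the nurse. It would be 13–19% (6–10% favouring the nurse) only if any one of four tests sufficed. Any success favouring the nurse would be about 3.6–5.2% if 15% is an absolute observed threshold for MMAS-4. There is no inflation if everything must succeed.

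All rates assume two-sided tests and the stated correlation ranges. The lower ends need correlations over time near 0.9.

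**What to change.** 1. In Section 3.2.1, replace the MMAS-4 mean with the proportion scoring below 2, and make MMAS-4 at day 30 secondary. Align the times in the Study Summary objective.
2. In Section 7.3, replace the sentence on readjustments with one rule that holds two-sided error at 0.05 for the primary conclusion:
   - name one primary time and test SPER and MMAS-4 there by Holm (smaller p-value against 0.025, then the other against 0.05); or
   - if both times stay primary and the scales support separate conclusions, test the two times within each scale by Holm (0.025, then 0.05), and state that error is controlled per scale and not across scales.
3. State whether the 15% is a planning difference or a success threshold, and whether it is absolute or relative.
4. Reconcile the description of the day-7 call as baseline in Section 3.1 with its use as a primary time in Section 7.1.

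**Cost.** Wording, and some power. At the first Holm step with 186 evaluable per arm, MMAS-4 power falls from 90% to 84% if 15% is absolute (about 77.5% with an assumed 15% loss), or from 54% to 42% if it is relative. The SPER difference detectable with 80% power rises from 0.58 to 0.64 points. Requiring both scales to succeed at one time also controls error, but it is a real trade-off: power is 72–75% if the SPER difference is 0.58, and 28–30% if it is the 0.3 named in Section 7.3 (15% absolute in both cases).

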7.4 Statistical Methods

In our primary analysis, we will first compare baseline demographics between groups. For our results section, we will compare all patients in the control group to all patients in the intervention arm for outcomes. Mean scores on the SPER will be compared between groups using student t-tests. We will compare proportions of adherent patients on the MMSA-4 between groups using the Pearson chi-square test. Total scores on the SIS, quality of life questions, and the 13 newly devised questions will be compared between groups using t-tests.

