3.1.2 Study Intervention Phase

All of the standard medical care will be identical in both arms of the study. Health literacy will be assessed in all patients upon admission to assure educational interventions are directed accordingly. Patients who

are assigned to standard nursing care will receive standard care which includes educational interventions from staff nurses in keeping with current Joint commission and AHA/ASA guidelines. Patients assigned to routine care will not interact with the attending nurse. Patients who are assigned to the intervention will receive additional patient-centered supplementary care and education from the attending nurse.

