3.1.3 Allocation to Interventional Group

Stroke patients who are admitted on even-numbered weekdays and enrolled in this trial will be assigned to care with an attending nurse; patients admitted on odd-numbered weekdays will get usual routine care. The attending nurse will query the electronic medical record as well as communicate with the physician team so that all incoming admissions on even-numbered days to the Vascular Neurology service are known to the attending nurse.

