5.2 Intervention Regimen

The attending nurse will spend 30 minutes to 45 minutes upon initial evaluation to determine the patients' goals, barriers, and needs. The amount of time spent with each subject following the initial visit will vary based on the patient. To limit the demands on the attending nurse, she will never carry a case load of more than 8 patients at a single time. If on an even-numbered weekday the attending nurse has 8 patients, than the subject will be assigned to the routine care arm of the trial. Patients who are assigned to the attending nurse model of care will be seen by that nurse on a daily (weekday) basis in addition to being cared for by their regular care team of physicians and rotating staff nurses. All staff nurses as well

as the attending nurse will participate in morning interdisciplinary table rounds in keeping with preexistent quality processes.

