6.2 Study Intervention Phase

If patients satisfy inclusion criteria and lack exclusion criteria they will be assigned to the intervention arm or the control arm depending on their admission date. The intervention phase will be the duration of the patient's hospital stay.

No research related procedures that differ from standard of care will be conducted as this is a comparative effectiveness trial.

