7.4.1 Baseline Data

Baseline and demographic characteristics will be summarized by standard descriptive statistics (including mean and standard deviation for continuous variables such as age and standard percentages for categorical variables such as gender). Stroke severity and PMH will also be collected and compared between the groups.

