7.5 Subject Population(s) for Analysis

The entire subject population who undergo treatment assignment will be studied primarily via intention to treat analysis comparing data from follow up phone calls between groups. An as-treated analysis will also be performed.

Analysis will be performed on some pre-defined subgroups where we may expect to see effect modification: major stroke vs. minor strokes (NIHSS \leq 5), multiple medications vs. few medications, patients who were admitted following a recurrent stroke vs. a new stroke, and hemorrhagic stroke vs. ischemic stroke subtypes.

8 Safety and Adverse Events

This protocol is extremely low risk as it assigns patients to already existent forms of inpatient care. This study does not include any experimental treatment. Given there is no proposed intervention or proposed management beyond two existing forms of standard clinical care, the routine collection of adverse events is not relevant, as those will be part of routine care. However, there may be a difference between the two arms in terms of specific events of interest. These specific events of interest include falls, aspiration pneumonia, and subsequent (post-discharge) major cardiovascular and cerebrovascular events (MACCE) including stroke (ischemic, hemorrhagic, or unknown), myocardial infarction, and death of any cause. Transfers to a higher level of care (e.g. to the Neuro ICU or medical ICU from the floor) that occur as part of routine care will also be considered events of interest. We will also report any unanticipated events.

All of the aforementioned events of particular interest will be assessed while the subject is in the hospital in keeping with standard clinical care. During follow up phone calls, the interviewee will ask patients and/or their family members specifically about the occurrence of MACCEs including and death of any cause.

The safety of each mode of nursing care while the subject is in-house will be tracked using the quality control processes that are already in place as part of standard inpatient care.

9 Study Administration, Data Handling and Record Keeping

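### SPER and MMAS-4 adherence are compared without prespecified covariate adjustment, and the caseload diversion rule conflicts with date-based assignment, leaving no analysis by admission date

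*Combined protocol and SAP*

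**What the plan says.** Section 7.4 states: "Mean scores on the SPER will be compared between groups using student t-tests". It compares the proportion adherent on the MMAS-4 by Pearson chi-square, and SIS, quality-of-life and survey totals by t-test. No section names a covariate, a regression model or an adjusted analysis.

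Patient data from the admission are collected. Section 7.4.1: "Stroke severity and PMH will also be collected and compared between the groups". Section 3.1.2 (Study Intervention Phase): "Health literacy will be assessed in all patients upon admission to assure educational interventions are directed accordingly". Table 1 schedules medical history, prior medications and a literacy screen. Their only stated analytic uses are the between-arm comparison and, for severity, medications, prior stroke and stroke type, the subgroups in 7.5.

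On arm membership, section 3.1.3 says "Stroke patients who are admitted on even-numbered weekdays and enrolled in this trial will be assigned to care with an attending nurse". Section 6.2 says of eligible patients that "they will be assigned to the intervention arm or the control arm depending on their admission date". Section 3.1 gives the same rule and defends it on the ground that nothing clinical or systematic otherwise goes with odd or even days. Section 5.2 adds an exception: if, on an even-numbered weekday, "the attending nurse has 8 patients, than the subject will be assigned to the routine care arm of the trial". Section 7.5 then says "The entire subject population who undergo treatment assignment will be studied primarily via intention to treat analysis" and "An as-treated analysis will also be performed". Neither 7.4 nor 7.5 mentions diverted patients.

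**The concern.** Date allocation is not randomisation, so chance is not the only possible source of imbalance. The plan itself treats admission factors as prognostic: 7.3 says SIS differences will depend on initial severity, and 1.1 cites the number of discharge medications as a predictor of persistence. A between-arm table can reveal an imbalance but does not correct the estimate, and choosing covariates after seeing that table would be data-driven. Prespecified adjustment for values already collected gains precision and guards against measured imbalance at almost no cost.

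The second issue is which comparison the trial makes. If diverted patients count as routine care, arm membership depends on nurse workload as well as date. The justification in 3.1 covers groups formed by date, not groups altered by caseload. The as-treated analysis does not restore the date comparison, because it also classes diverted patients as routine care.

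**Working it through.** **Inputs.** From 7.3: 186 per arm, alpha 0.05 (taken as two-sided), power 80%, SPER SD 2 and difference 0.3, control adherence 65%, improvement 15% (taken as absolute, to 80%). From 4.5: about 7 months' recruitment (213 days) and 700-800 stroke admissions a year. From 5.2: a cap of 8. Assumed, because the documents do not give them: R2, mean stay, and how diverted patients differ. No losses are assumed.

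**The plan's own figures.** The standard two-proportion formula for 65% against 80% gives 138 per arm (151 with continuity correction), not 186. At 186 per arm, 0.3 SPER points has 30% power. Both are separate issues; 186 is used below as the planned size.

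**Precision, SPER.** SE = 2 × sqrt(2/186) = 0.207. Detectable difference at 80% power = 2.802 × 0.207 = 0.58. Adjustment multiplies the SE by sqrt(1 − R2).

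| Assumed R2 | Detectable difference | Power at 0.3 |
|---|---|---|
| 0 | 0.58 | 30% |
| 10% | 0.55 | 33% |
| 20% | 0.52 | 37% |
| 30% | 0.49 | 41% |

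**Precision, MMAS-4.** With unpooled variance, the detectable difference falls from 13.0 to 12.7, 12.4 and 12.0 points at R2 of 5%, 10% and 15%.

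**Share diverted.** Treat the nurse as 8 places with load A = arrivals per day × mean stay. The Erlang loss formula gives f = (A^8/8!) / Σ(A^k/k!), k = 0 to 8. If only enrolled patients load the nurse, arrivals are 186/213 = 0.87 per day. If all admissions do, arrivals are 350/365 = 0.96 to 400/365 = 1.10 per day.

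| Assumed mean stay | Enrolled only | All admissions |
|---|---|---|
| 4 days | 1.7% | 2.5-4.4% |
| 6 days | 8.2% | 11-15% |
| 8 days | 17.8% | 22-28% |

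Allowing arrivals on alternate days only (simulated, enrolled only) gives 1.9%, 8.5% and 18%.

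**Possible bias if 5.2 defines the arm.** Suppose odd and even days have the same mix, and diverted patients differ from other even-day patients by D SD on a covariate. The between-arm imbalance is then D × 2f/(1+f). With D = 0.5 (assumed), correlation 0.3 with SPER (assumed) and SD 2, the bias is 0.3 × 2 × imbalance.

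| f | Imbalance (SD) | SPER bias (points) | Share of 0.58 |
|---|---|---|---|
| 2% | 0.02 | 0.01 | 2% |
| 8% | 0.07 | 0.04 | 8% |
| 18% | 0.15 | 0.09 | 16% |
| 28% | 0.22 | 0.13 | 23% |

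**Cost of analysing by date.** With no effect in diverted patients, a 15-point MMAS-4 effect becomes 15 × (1 − f). Power, unpooled, is Φ(difference/SE − 1.96), where SE = sqrt[(0.65 × 0.35 + p(1 − p))/186] and p = 0.65 + difference.

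| f | Difference (points) | Power |
|---|---|---|
| 0 | 15.0 | 91% |
| 2% | 14.7 | 90% |
| 8% | 13.8 | 85% |
| 18% | 12.3 | 75% |
| 28% | 10.8 | 63% |

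Analysing diverted patients as routine care costs almost no power: at 18% diverted, arms of about 153 and 219 give 89% with pooled variance, against 90% with equal arms.

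**Model size.** Expected non-adherent patients: 186 × 0.35 + 186 × 0.20 = 102. With 8 coefficients (arm, NIHSS, literacy, age, two for diagnosis type, prior stroke, medication count) that is about 12.8 each.

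**The case against.** A prespecified t-test and chi-square are legitimate and answer the stated objective. Every R2 above is assumed, the precision gain is small, and 7.3 calls the study a pilot. That stands: omitting adjustment is not an error that invalidates the analysis. It is a cheap improvement left out where allocation is not random.

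A reader might infer that the plan is silent on diverted patients. The documents do not support this. Section 5.2 assigns them to routine care, and 7.5 bases intention to treat on assignment, so routine care is the natural reading. What remains is the conflict with the unqualified date rule elsewhere and the absence of any analysis by date.

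A reader might also infer that diversion biases the trial. Nothing in the documents shows that diverted patients differ; the trigger in 5.2 is caseload, not a patient characteristic. Nor is comparison by date the only remedy for unmeasured differences, since caseload or calendar period at admission could be modelled. Analysis by date also dilutes the effect, so it belongs as a sensitivity analysis. Finally, the diversion figures depend heavily on assumed stay and on who loads the nurse, and serve only as a range.

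**Conclusion.** The point holds in two limited parts. First, the primary endpoints have no prespecified adjustment although suitable admission data are collected. The gain is modest, 0.58 to between 0.55 and 0.49 SPER points at assumed R2 of 10-30%, plus protection against measured imbalance. It does not rescue SPER power, which stays at or below 41% for 0.3 points, and it does not replace randomisation.

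Second, 5.2 conflicts with 3.1, 3.1.3 and 6.2. On the reading that 5.2 and 7.5 imply, no planned analysis compares patients by admission date, the only grouping that the argument in 3.1 covers. Whether this matters depends on the share diverted: roughly 2-4%, 8-15% or 18-28% at assumed mean stays of 4, 6 or 8 days. Any resulting bias may be negligible. The change should be made, but the trial's validity does not turn on it.

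**What to change.** In 7.4, prespecify linear regression for SPER (and SIS), and logistic regression reported as a standardised risk difference for MMAS-4 below 2. Include arm and a short fixed list of admission values: NIHSS, age, diagnosis type and prior stroke, plus pre-admission medication count for MMAS-4. Include admission health literacy only if it is recorded before the attending nurse's first visit; Table 1 places the screen in the same column as allocation, so its timing needs stating. Use no day-7 value as a covariate, although 3.1 calls the day-7 call the baseline. State how missing covariates are handled. Keep the t-test and chi-square as supportive.

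Reconcile 3.1, 3.1.3 and 6.2 with 5.2 by stating which rule defines the intention-to-treat arm. Add a sensitivity analysis by admission-date parity that keeps diverted patients in the even-day group, saying how weekend admissions are classed, and report the number diverted. The caseload cap itself is not questioned.

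Cost: SAP wording and a little more analysis. Section 9.2 should name NIHSS, admission literacy, diagnosis type and pre-admission medication count; other sections already imply that severity, literacy, stroke type and medications are recorded. Hospital-stay dates are already abstracted. No new patient assessment is needed. The parity analysis carries the dilution shown above.
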